3.7. Informed Consent Process

Patients under the care of the study investigators will be provided with the written informed consent form with plain language information about the research. The study will be explained to potential subjects, and they will be advised that participation is voluntary. Potential subjects will have the opportunity to ask questions of the study investigator before agreeing to participate and signing the consent form. Patients will not be coerced into the study. Any patient that chooses not to consent will undergo the standard microsurgical procedure and their health care will not be compromised in any way. Patients shall be free to withdraw from the study at any time.

3.8. Monitoring and Execution of the Trial

The Sponsor's Obligations are outlined in Appendix 1 of this document.

The Investigator's Agreement and Obligations are outlined in Appendix 2 of this document

The results, progress and execution of the feasibility study will be monitored as outlined in chapter 4.5.10 (Microscope imaging during YE560 fluorescence use).

Carl Zeiss Meditec, Inc. (or designee)

[name]

[name]

The clinical investigation team will meet quarterly during active enrollment to review enrollment, current outcomes and any adverse events.

3.9. Record Keeping

Clinical investigators shall keep a record of subjects recruited in a secure database and/or spreadsheet, and study participation will be recorded in each patient's medical case notes stored by the hospital. Case report forms, images and other associated procedure data labelled with the patient's 3 digit code shall be provided to the Sponsor for analysis and back up. All required records will be stored by the Sponsor and Investigators for a period of 3 years after completion of the study.

4. Description of the Medical Device under Investigation

4.2. Item/Part Number

The microscope equipped with the YE560 fluorescence module for clinical evaluation comprises:

- **Surgical Microscope**

Name: Kinevo 900

- **Fluorescence module**

Name: YELLOW 560

REF: 303582-9205-000

- **Still Image and Video recording**

Name: Video Recording HD

REF: 303582-9700-000

- **Capturing device**

Name: High Definition Camera 3CCD NTSC

REF: 303581-9764-000

4.3. Intended Purpose of this Device

The Kinevo 900 with YE560 fluorescence option is a surgical microscope equipped with an visualization tool to detect fluorescence signals in a wave length range between 540nm to 690nm.

4.4. Clinical Indications & Contraindications for use in Study

The clinical indication for use of the YE560 fluorescence module in the proposed study is neurological pathology requiring open craniotomy or translabyrinthine otologic approach.

Use of the YE560 fluorescence option is contra-indicated in patients where the tumor resection bed is not directly surgically exposed and cannot be visualized with the surgical microscope.

A fluorescent contrast agent, FS will be administered intravenously within its labeled dose range for its approved use in ophthalmic applications to reveal fluorescence contrast during the use of YE560.

Occasionally patients may experience adverse events. The fluorescein dye can rarely cause allergic reactions. Fluorescein dye is a FDA-approved medicine that is routinely used by ophthalmologists (eye doctors) to perform exams of the retina of the eye. Administration of Fluorescein is contraindicated in patients with:

- Known allergy or prior adverse reaction to Fluorescein
- Women who are pregnant or breastfeeding

4.5. Summary of Device Design

The Instruction for use covers basic set-up and use of the KINEVO 900 equipped with YE560 fluorescence option

The YE560 option is an accessory for intra- operative illumination of the surgical field with light of a wavelength between 460nm and 690nm.

The integrated fluorescence module YE560 serves to make fluorescent areas visible. It is designed for stimulus light penetrating the service in a wave length range from 460nm to 500nm and for visualizing the YE560 fluorescence light reflected by the service in a wave length range of 540nm to 690nm.

Surgeons can switch between white light and fluorescence mode. Blue excitation light should be dimmed for optimum reproduction of the fluorescence light.

The YE560 lighting option can be operated from the hand grip or foot switch. The user manual explains how to set-up, operate and record images taken with the YE560 module.

5. Training and Experience Requirements for use of the Device

The Instruction for use covers basic set-up and use of the YE560 fluorescence option as well as recording function for capturing pictures. Training in the use of YE560 for all operating surgeons in this study will be provided by the Sponsor representative before use in surgery on enrolled subjects. A training log documenting personnel and training dates will be kept by the study coordinator. All study cases will be assisted by a sponsor representative.

[figure not shown]
6. Description of Medical/Surgical Procedures involved in the use of the device

The YE560 fluorescence option will be used during open craniotomy procedures performed for the purpose of tumor resection and possible biopsy. Standard neurosurgical techniques shall be used throughout the procedure. The YE560 fluorescence will be used during the surgery, once the tumor is exposed. The YE560 fluorescence visualization option can be turned on/off during the tumor resection phase of the surgery. Images captured with the KINEVO 900 under YE560 light and simultaneously navigation pictures, representing the location of the biopsy during surgery will be linked to the biopsy results available after surgery. To obtain images, a fluorescent contrast agent is required. Fluorescein Sodium will be administered intravenously prior to imaging within its labelled dose range for its approved use in ophthalmic applications to reveal fluorescence contrast during the use of YE560.

7. Study Drug

7.1. Description

AK-FLUOR® (fluorescein injection, USP) 10% contains fluorescein sodium (equivalent to fluorescein 10% w/v). It is a sterile solution for use intravenously as a diagnostic aid. Its chemical name is spiro[isobenzofuran-1(3H), 9'-[9H]xanthene]-3-one, 3'6'-dihydroxy, disodium salt. The active ingredient is represented by the chemical structure (Figure 2):

376.27 MW

Figure 2 Fluorescein 10%

AK-Fluor® (fluorescein injection, USP) 10% is supplied as a sterile, unpreserved, single-use aqueous solution, that has a pH of 8.0 - 9.8 and an osmolality of 572-858 mOsm/kg. Active ingredient: fluorescein sodium Inactive Ingredients Sodium hydroxide and/or hydrochloric acid (to adjust pH), and water for injection.

7.2. Method for Assigning Subjects to Study Group

Patients under the care of the Clinical Investigators who are clinically indicated for surgical resection as a suspected VS or recurrent VS will be considered eligible for participation in the study. Investigators will determine if patients are eligible for the study during clinic appointments. Each potential participant will be assessed against the inclusion and exclusion criteria. Potential participants shall be provided with plain language information about the study on the IRB-approved consent form and will have the opportunity to ask questions of the study investigators. Informed consent shall be obtained by the Principal Investigator, Co-Investigators, or research coordinator from eligible patients wishing to participate. Any patient who chooses not to participate in the study will undergo their indicated microsurgery with standard techniques, and their health care will not be compromised in any way. Participants shall be free to withdraw from the study at any time. Participants will be withdrawn if their intraoperative biopsy yields an entity other than VS.

7.3. Preparation and Administration of Study Drug

The preparation and administration of fluorescein sodium is coordinated and executed by the anaesthesiologist responsible during the surgery according to dosage and administration recommended indicated by the product insert.

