Intraoperative fluorescence imaging has been utilized in the resection of HNP and meningiomas. Indocyaninegreen fluorescence angiography has been used to assess post-embolization vascularity of paraganglioma to estimate bleeding risk.⁸ FS has been utilized with the YE560 to distinguish meningioma and hyperostosis from surrounding brain and healthy bone.⁹

FS is FDA approved for ophthalmologic applications. The standard dose for retinal imaging in adults is a 500 mg bolus into a peripheral vein (7.1 mg/kg in a 70 kg patient).¹⁰ The safety profile of intravenous FS is well-described in the ophthalmology literature. Nausea and vomiting are the most common side effect reported, but 87% of surveyed ophthalmologists reported rates less than 5%. Urticaria is estimated to occur at a rate of 1 in 82 patients. Severe adverse reactions, including respiratory reactions (1:3,800), cardiac events (1:5300), and tonic-clonic seizure (1:13,900) are rare and estimated to occur cumulatively in 1 in 1900 patients.¹¹

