3.4. Hypothesis

12. Given prior evidence of preferential uptake of FS in VS and meningiomas due to disrupted blood brain barrier, we hypothesize that use of intravenous FS will allow for visual differentiation of tumor and surrounding structures and nerves using YE560.
13. The optimal dosing for FS has not been established for this application. Pedro et al utilized 0.5-1.0 mg/kg body weight to visualize peripheral nerve sheath tumors with YE560. The authors found saturation of all tissues with 3-4 mg/kg dose within 18 seconds of administration. The blood-brain barrier may play a modulating role. Schebesch et al (2013) used 3-4 mg/kg to visualize malignant gliomas and observed fluorescence after 20-30 minutes. We suspect that the optimal dose will be 3-4 mg/kg, and peak fluorescence will take a similar amount of time. However, we will initially utilize 1.0 mg/kg SF administered at the time of first visualizing the tumor to enable subsequent doses (up to a maximum of 500 mg or 7 mg/kg). This will allow us

to determine the minimum effective dose and observe the time to peak fluorescence. The optimal dosing strategy will be finalized after the first 10 cases.

14. We hypothesize that the surgeons will be satisfied with the use of SF and YE560, as reflected in responses on the Surgeon Survey. Specifically, we hypothesize that greater than 75% of surgeons would choose to use SF and YE560 at least in the majority of future VS, meningioma, HNP, or HNS resections based on responses from the Surgeon Survey. Secondarily, we hypothesize that surgeons will rate the correlation of fluorescence with visual assessment with white light microscopy and electrostimulation to be “good” or “excellent” for over 75% of the cases.
15. Because the yellow fluorescence is primarily comprised of red and green components, we hypothesize that RGB component analysis of intraoperative images will yield significantly higher red and green values in the VS compared to the facial and cochlear nerves. Similar analysis may be conducted between the tumor and surround nerves or structures of interest for meningiomas, HNP, and HNS.

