3.6.11. Microscope imaging during YE560 fluorescence use

1. Standard methods of anesthesia as appropriate for open craniotomy or otologic surgery will be used.
2. Surgeons will gain access to the lesion of interest through a craniotomy or translabyrinthine approach.

3. At the time of tumor exposure, patients will be given intravenous FS. The timing and dose may vary. Maximum cumulative dose will not exceed 500 mg.

- Initial dosing protocol will be 1 mg/kg intravenous FS.
 - If insufficient fluorescence is obtained or washout occurs, additional doses of 1 mg/kg may be administered
- Based on the experience of the first 3 cases, modifications to the dosing protocol may be made.
 - A higher, single dose may be administered if there is insufficient fluorescence or premature washout. Additional doses may be given during surgery.
 - If saturation of normal tissue with fluorescence occurs, the dose may be decreased or the FS may be administered at an earlier time point (opening of dura, anesthesia induction, etc.) during subsequent cases
- Continued adjustments may be made to the dosing and timing, with a goal of standardizing the dose after 10 cases

4. Once the VS has been surgically exposed and FS has been administered, the YE560 fluorescence module shall be used to visualize fluorescence in the tissue. Images will be captured prior to tumor dissection, after exposure of the intracapsular tumor contents, and after maximum resection. A pair of images—one using the YE560 and one with white light microscopy—will be captured during each event.

5. With the YE560 turned on, images will be captured with the microscope. Video recording from the Pentero 900 and Kinevo 900 microscopes will be captured for the entirety of their use in the case.

6. The time from injection until to the point where the differential fluorescence is greatest will be recorded and documented in the surgeon's survey. Circulating nursing staff will record timestamps in collaboration with instruction from the operating surgeons.

7. The YE560 module will be applied during the aforementioned events and additionally at the discretion of the operating surgeons. Depending upon the number of potential regions identified for imaging and for possible biopsies, the YE560 fluorescence module is expected to add less than 10 minutes to the overall procedure.

8. At any time, the operating surgeon may turn off the YE560 module as dictated by the needs of surgery.

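### Section 7.3 tells the anaesthesiologist to dose fluorescein by the product insert, against the 1 mg/kg titration in Sections 3.4 and 3.6.11, and no clause says which governs

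*Protocol*

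**What the plan says.** Section 7.3 names the responsible anaesthesiologist as the person who prepares and gives fluorescein, and says this is done "according to dosage and administration recommended indicated by the product insert". It mentions neither the study's dosing scheme nor Section 3.6.11.

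The study's own scheme is in two other places:

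- **Section 3.4:** "we will initially utilize 1.0 mg/kg SF administered at the time of first visualizing the tumor". The low start is meant to leave room for further doses, so that the minimum effective dose and the time to peak fluorescence can be found. The same section adds: "We suspect that the optimal dose will be 3-4 mg/kg".
- **Section 3.6.11:** "At the time of tumor exposure, patients will be given intravenous FS"; "Initial dosing protocol will be 1 mg/kg intravenous FS". Further 1 mg/kg doses are allowed if fluorescence is insufficient or washes out. "Based on the experience of the first 3 cases, modifications to the dosing protocol may be made", and the aim is a standard dose after 10 cases. The ceiling is "Maximum cumulative dose will not exceed 500 mg".

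On the approved ophthalmic use, Section 3.2 says "The standard dose for retinal imaging in adults is a 500 mg bolus into a peripheral vein", which it converts to 7.1 mg/kg at 70 kg. Section 3.5 treats the same 500 mg as the cumulative maximum. Sections 4.4 and 6 say only that dosing stays inside the labelled range.

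**The concern.** Two instructions cover the same act. The one in the study-drug section, addressed to the person holding the syringe, points to the insert's recommended dosage. The one in the methods sections points to a titrated 1 mg/kg start. They agree only if the insert happens to recommend the study's dose, and the protocol gives no reason to expect that: Section 3.4 says no optimal dose has been established for this use.

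Finding the optimum dose and timing is a secondary objective (Section 3.1), and the low start is how the plan pursues it. A patient given a full ophthalmic bolus at the outset cannot be titrated upward, and shows nothing about the minimum effective dose or the time to peak after a low dose. The clash also blurs what counts as a deviation. Where the two schemes differ, following one departs from the other, and Appendix 2 requires deviations from the investigational plan to be documented and reported to the sponsor.

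**Working it through.** **Inputs.** Start dose 1 mg/kg (Sections 3.4, 3.6.11). Suspected optimum 3–4 mg/kg (Section 3.4). Cumulative cap 500 mg (Sections 3.5, 3.6.11). Standard adult ophthalmic dose 500 mg, or 7.1 mg/kg at 70 kg (Section 3.2). Sample size 90 (Section 3.5). Vial: 5 mL of a 10% solution (Sections 7.1, 7.5). The insert's recommended dose is not given, so it is treated as an assumption.

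**Reproducing the plan's figure.** 500 mg / 70 kg = 7.14 mg/kg, which rounds to the stated 7.1.

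**If the insert dose is 500 mg, at 70 kg:**

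- Against the start: 7.14 / 1 = 7.1 times (500 mg instead of 70 mg).
- Against the suspected optimum: 7.14 / 4 = 1.8 times to 7.14 / 3 = 2.4 times.
- Allowance left for titration: 500 − 500 = 0 mg.

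**Other body weights (assumed), 500 mg bolus against a 1 mg/kg start:**

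| Weight | 1 mg/kg start | 500 mg bolus | Ratio to start |
|---|---|---|---|
| 50 kg | 50 mg | 10.0 mg/kg | 10.0 |
| 70 kg | 70 mg | 7.14 mg/kg | 7.1 |
| 100 kg | 100 mg | 5.0 mg/kg | 5.0 |
| 120 kg | 120 mg | 4.17 mg/kg | 4.2 |

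At each of these weights the bolus is above 4 mg/kg, the top of the 3–4 mg/kg range at which Section 3.4 reports saturation of all tissues in the cited peripheral nerve sheath tumor series.

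**Other insert doses (assumed), at 70 kg.** 100 / 70 = 1.4 times the start; 250 / 70 = 3.6 times; 500 / 70 = 7.1 times. At the low end the conflict in amount is small.

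**Vial content.** 10% w/v is 100 mg/mL, so 5 mL × 100 mg/mL = 500 mg. One single-use vial holds the whole standard bolus, whereas the 70 mg start is 0.7 mL.

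**Second ceiling.** Section 3.4 also words the maximum as 500 mg or 7 mg/kg. Since 500 / 7 = 71.4 kg, a 500 mg bolus exceeds 7 mg/kg in any patient lighter than that.

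**Reach.** The 1 mg/kg start is fixed for the first 3 cases: 3 / 90 = 3.3%. Dose finding is meant to end by case 10: 10 / 90 = 11.1%. These count the cases in which a wrong dose would damage the dose-finding aim. They do not estimate how many would be misdosed.

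**Wording side by side.** Where the protocol means the label as a limit (Sections 3.5, 4.4 and 6), it speaks of a range or a maximum. Section 7.3 speaks of the recommended dosage. It therefore cannot be read as another statement of the ceiling without changing its words.

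**The case against.** The strongest reply is that the conflict in amount depends on a document nobody has shown. The 500 mg figure in Section 3.2 is cited to an online drug summary whose address names a different fluorescein brand, while the study drug is AK-Fluor. Three other sections treat the label as an outer limit, and 7.3 sits among routine supply and handling paragraphs, so it may mean only who gives the drug and that handling follows the label. The study dose is set out at length in 3.4 and 3.6.11, and the Appendix 3 survey has mg/kg lines for first, second and third doses, which make sense only under titration. A sponsor representative assists every case (Section 5), investigator training covers contrast agents and workflow (Section 8.2), and a full-bolus error would show in that case's survey before the next patient.

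Much of this stands. Staff would probably follow 3.6.11, the dose would stay within 500 mg, a higher single dose is permitted after case 3, and the affected aim is descriptive. What does not stand is the claim that 7.3 needs no correction. It names dosage explicitly, no other section overrides it, and the described training is for surgeons and clinical investigators, with none specified for anaesthesia staff. The missing insert makes the size uncertain; it does not reconcile the two instructions.

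**Conclusion.** The point holds and should be fixed. The clash in wording is certain: 7.3 directs dosing by the insert, 3.4 and 3.6.11 direct a titrated 1 mg/kg start, and nothing ranks them. Its size is conditional. On the protocol's own account of the standard adult dose (500 mg) and at 70 kg, following 7.3 literally gives about 7 times the intended start and leaves nothing to titrate with. Over assumed insert doses of 100 to 500 mg, the ratio runs from 1.4 to 7.1. The damage to dose finding is confined to the first 3 cases and at most the first 10 of 90. The contradiction in the text lasts longer if the standardized dose differs from the insert. No breach of the 500 mg cap and no effect on the primary endpoint is claimed.

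**What to change.** Amend Section 7.3 to say that the product insert governs preparation, handling and route only, and that dose and timing follow Section 3.6.11 as directed by the operating surgeon, within the 500 mg cumulative cap. The cost is one sentence with a cross-reference; no extra patients, procedures or data are needed.

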7.4. Subject Compliance and Adverse Event Monitoring

7.4.1. Adverse Event Monitoring

Adverse events (AEs) must be reported on the Adverse Event Form (AEF). Adverse events that will be monitored include urticaria, anaphylaxis, respiratory compromise, cardiac events, seizure, and death. These events will be monitored in the first 3 months after surgery. Complete clearance of SF is expected within 72 hours, and associated adverse events, if any, are anticipated within that timeframe. After discharge from the hospital, any reporting of adverse events will rely upon participants contacting the research team prior to the scheduled 3 month follow up. Nausea and vomiting will not be included as an adverse event as these symptoms are expected outcomes from surgery.

If adverse events occur, the first concern will be the safety and welfare of the patient. Appropriate medical intervention will be made. Any adverse events observed by the Investigator or reported by the patients will be recorded in the appropriate section of the patient's Case Report Form (CRF) as well as on an Adverse Event Form.

The Investigator must categorize each AE by degree of harm to the patient (mild, moderate, or serious), and the relationship to study device (not related, possibly, probably, or definitely) in the Adverse Event Form. Adverse events observed will be captured on the Adverse Event Follow-up Form and the CRF until such time the adverse event is reported as resolved, or for the course of the study if the event does not resolve.

A serious adverse event includes any prolong hospitalization, and any event that is life-threatening, results in permanent impairment of a bodily function or permanent damage to a body structure, or an event that necessitates medical or surgical intervention to preclude such permanent impairment or permanent damage.

Changes in any chronic condition or disease that are consistent with natural disease progression are not considered AEs and will not be recorded on an AE CRF.

Medical treatment related to any adverse events will not be paid for by the study, Mayo Clinic, or the Sponsor. Patients and their insurance will be billed for any treatments or encounters associated with an adverse event.

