3.6.10. Primary safety endpoints

As FS is approved for the intravenous injection for ophthalmological applications and the safety profiles are well characterized and considered low risk. As described above the most common side effects are nausea and vomiting. This side effect is commonly experienced with resection of vestibular schwannoma due to transection of the vestibular nerve and resulting vertigo. Thus, this side effect will not be tracked or reported. Other adverse effects of SF—urticaria, anaphylaxis, seizure, cardiac events, respiratory compromise—will be tracked and reported up to 3 months after surgery. The relevance of the adverse event to the administration of SF will be determined by the principal investigator.

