9. Following completion of tumor resection and prior to closing of the dura, supramaximal and minimum stimulation values will be obtained (if relevant), as is standard practice with vestibular schwannoma microsurgery at our institution. The process is as described in Schmitt et al. (2013). In brief, transcutaneous bipolar electrodes are used at the extratemporal main trunk of the facial nerve to stimulate the nerve at 100 msec pulses increasing from 0 mA until a plateau amplitude compound muscle action potential is obtained. A Prass probe is used to stimulate the facial nerve proximal to the tumor (at the brainstem if possible) at increasing current (starting at 0 mA) until a plateau of CMAP is obtained. The ratio of these amplitude responses is calculated and subtracted from 1 to calculate the supramaximal stimulation. The minimum stimulation is the minimum current level at which a reliable facian nerve response can be obtained with proximal stimulation of the facial nerve using the Prass probe.

11. Suspected lesions that are found to be a histopathological entity excluded from this study after microsurgical resection and biopsy will be withdrawn from the study.

12. Post-procedure data analysis will include analysis of surgeon survey responses and, red/green/blue component analysis using ImageJ software. Additional data (demographics, imaging characteristics, facial nerve and audiometric data) will be reviewed and recorded from preoperative and 3 month postoperative visits. Video recordings will be edited to 30-60 second videos following the case with

representative views of the VS, facial nerve and cochlear nerve with and without the YE560 active. These edited videos will be used for the aforementioned surgeon validation study rating the correlation of fluorescence with white light microscopy.

13. Upon completion of surgery, operating surgeons will complete the remainder of the paper survey (Appendix 3). The surveys will be collected, with responses logged in the Rave database. The paper surveys will be stored in a secure location in the Otolaryngology department.

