7.4.2. Adverse Event Reporting

Any serious adverse events, whether unanticipated or not, and whether or not ascribed to study device, will be communicated promptly to Carl Zeiss Meditec Inc and to the IRB. These reports must be confirmed in writing within 5 days of the occurrence.

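### Adverse events are to be followed for 3 months, but capture after discharge is passive and the 5-day serious-event clock runs from occurrence, so later events may be missed or reported late

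*Protocol*

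**What the plan says.** Section 3.6.10 (Primary safety endpoints) names the reactions of interest and says they "will be tracked and reported up to 3 months after surgery". Section 7.4.1 gives the fuller list: "Adverse events that will be monitored include urticaria, anaphylaxis, respiratory compromise, cardiac events, seizure, and death". It repeats the window: "These events will be monitored in the first 3 months after surgery".

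The same paragraph of 7.4.1 then fixes how events are found once the patient has gone home: "After discharge from the hospital, any reporting of adverse events will rely upon participants contacting the research team". The sentence goes on to limit this to the time before the visit, so that reporting "will rely upon participants contacting the research team prior to the scheduled 3 month follow up". It also gives the expected timing of dye effects: "Complete clearance of SF is expected within 72 hours, and associated adverse events, if any, are anticipated within that timeframe". Elsewhere in 7.4.1, events that the investigator observes or the patient reports are to be recorded on the case report form and the Adverse Event Form.

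The 3-month visit appears in 3.6.9, 3.6.11 and 7.4.1. Item 12 of 3.6.11 names the additional data to be taken from it: demographics, imaging characteristics, and "facial nerve and audiometric data) will be reviewed and recorded from preoperative and 3 month postoperative visits". Adverse events are not in that list.

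Section 7.4.2 requires every serious adverse event, related to the device or not, to be passed promptly to the sponsor and the IRB, and adds: "These reports must be confirmed in writing within 5 days of the occurrence". Under Appendix 2, the investigator's report of an unanticipated adverse device effect is due within 10 working days of first learning of it.

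**The concern.** There are two separate problems.

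**Ascertainment.** A 3-month window is useful only if something looks for events throughout it. Between discharge and the visit, the protocol relies on the participant to make contact. That suits some of the listed events badly. A participant cannot report his or her own death, and a seizure or respiratory event may prevent a call. If nobody asks a standard question at 3 months, a blank record may mean that no event occurred or that none was mentioned. No later analysis can recover an event that was never collected, so this is a matter for the protocol.

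**Reporting clock.** A deadline counted from occurrence assumes that the team learns of the event almost at once. Passive capture does not ensure this. A team that acts on the day it hears of an event can still be out of compliance.

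**Working it through.** The protocol derives no safety sample size or precision, so no stated figure is in dispute. The check is mainly a comparison of the sections, with some arithmetic for scale.

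**1. Who looks for events, and when**

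| Period | Method stated | Source |
|---|---|---|
| In hospital | Investigator observation and patient report | 7.4.1 |
| Discharge to 3-month visit | Participant contacts the team | 7.4.1 |
| At 3-month visit | Observed or reported events are recorded; no set questions specified | 7.4.1; 3.6.11 item 12 |

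Only the middle row is purely passive. The last row gives a chance to recover events, but no procedure for doing so.

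**2. How much of the risk falls in the passive period**

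In calendar time, with 3 months taken as 91 days, the 72 hours in which dye effects are expected cover 3/91 = 3.3% of the window. Calendar time is not risk, however. If 7.4.1 is right about timing, most dye-related events fall in those first days. How many of those days are spent in hospital is unknown, because length of stay is not given. The exposed events are therefore mainly later or unrelated ones.

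**3. Scale of expected events**

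Section 3.2 gives respiratory reactions as 1 in 3,800, cardiac events as 1 in 5,300, seizures as 1 in 13,900, and about 1 in 1,900 together. The sum is 1/3,800 + 1/5,300 + 1/13,900 = 0.000524, or 1 in 1,909, which agrees.

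With 90 patients:
- expected severe dye reactions: 90/1,900 = 0.047
- chance of at least one: 1 − (1 − 1/1,900)^90 = 4.6%
- expected urticaria at 1 in 82: 90/82 = 1.1

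Counts will be very small, so a zero is a likely result for severe reactions and its meaning depends on capture.

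**4. What a post-discharge zero would mean**

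With 0 events recorded in 90 patients and full capture, the one-sided 95% upper bound on the rate is 1 − 0.05^(1/90) = 3.3%. If only a fraction c of post-discharge events is captured, the recorded rate is c times the true rate, and the bound becomes 3.3%/c. The documents give no c, so these values are assumptions:

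| Assumed c | Upper bound |
|---|---|
| 100% | 3.3% |
| 75% | 4.4% |
| 50% | 6.5% |
| 25% | 13.1% |

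This shows sensitivity only. It is not evidence that events will be lost, and it does not apply to in-hospital events.

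**5. The 5-day deadline**

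An event on day d that is first learned of at the visit on day 91 has a lag of 91 − d days. The lag exceeds 5 when d is below 86. For an assumed discharge on day L, the share of the post-discharge period in which such an event is already late is (86 − L)/(91 − L):
- L = 3: 83/88 = 94.3%
- L = 5: 81/86 = 94.2%
- L = 7: 79/84 = 94.0%

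This applies only to events that first surface at the visit. An event in hospital, or one phoned in promptly, has a short lag and can comply.

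**The case against.** The strongest reply is that the reliance on patient contact is expressly limited to the time before a scheduled visit, and that an event observed or mentioned at that visit would be recorded under 7.4.1. Item 12 of 3.6.11 sits in the imaging section and lists data for analysis; it is not a complete visit schedule. The case report form is not shown and may already prompt for the six events. The study is a largely descriptive feasibility study (3.5) of a dye that is FDA-approved for ophthalmologic use, with reactions expected within 72 hours. The protocol states its passive method openly. Section 3.8 also provides for quarterly review of adverse events during enrollment.

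Much of this stands. A reader might infer that the 3-month count is certain to be incomplete, or that event rates will be biased downward. The documents do not support either. The visit can recover events, no event rate or safety threshold is defined, and the extent of any loss is unknown. A reader might also infer that the deadline can never be met, or that 7.4.2 contradicts Appendix 2. Neither follows. In-hospital and promptly reported events can comply, and Appendix 2 governs a different report with a different time limit.

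The reply does not remove two things. The text specifies no adverse event questioning at 3 months, and death cannot be self-reported. The quarterly meeting reviews events already known and does not find new ones.

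**Conclusion.** The point holds in a limited form. The post-discharge part of the 3-month count is liable to under-ascertainment, mainly for later events and those unrelated to the dye. The amount cannot be estimated from the documents. The 5-day written confirmation cannot be met for a serious event first learned of more than 5 days after it happened. The protocol takes an awareness-based approach for unanticipated device effects, so its approach to timing is inconsistent across the two duties.

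This rests on three readings: 3 months is about 91 days; the visit has no set adverse event questions beyond what the text shows; and the 72-hour expectation for dye effects is correct. If the case report form already prompts for all six events, the ascertainment half reduces to saying so in 7.4.1. The primary endpoint, the surgeon survey, is unaffected. This is a cheap improvement, not a flaw that threatens the study.

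**What to change.** In 7.4.1, add to the 3-month visit already scheduled a fixed checklist of the six monitored events, with a yes or no recorded for each, and a chart review covering discharge to that visit. The chart review also offers a route to deaths and to events that a patient could not report. Present in-hospital and post-discharge events separately, so that a reader can see which counts came from direct observation.

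In 7.4.2, count the 5 days for written confirmation from when the investigator learns of the event, and record both the occurrence date and the awareness date.

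The cost is a few minutes per patient at an existing visit and one changed line in 7.4.2. No extra visit is needed.
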